7.2.2 Pembrolizumab Supportive Care Guidelines

Patients should receive appropriate supportive care measures as deemed necessary by the treating investigator. Suggested supportive care measures for the management of AEs with potential immunologic etiology are also outlined in the table in Section 7.1.3. Where appropriate, these guidelines include the use of oral or IV treatment with corticosteroids as well as additional anti-inflammatory agents if symptoms do not improve with administration of corticosteroids. Note that several courses of steroid tapering may be necessary as symptoms may worsen when the steroid dose is decreased. For each disorder, attempts should be made to rule out other causes such as metastatic disease or bacterial or viral infection, which might require additional supportive care. The treatment guidelines are intended to be applied when the investigator determines the events to be related to Pembrolizumab.

Note: If after the evaluation the event is determined not to be related, the investigator does not need to follow the treatment guidance (as outlined below).

It may be necessary to perform conditional procedures such as bronchoscopy, endoscopy, or skin photography as part of the evaluation of the event.

7.2.3 Recognition and Treatment of Early Immune Related Events

Subjects should receive appropriate supportive care measures as deemed necessary by the treating investigator. Suggested supportive care measures for the management of adverse events with potential immunologic etiology are outlined below. Where appropriate, these guidelines include the use of oral or intravenous treatment with corticosteroids as well as additional anti-inflammatory agents if symptoms do not improve with administration of corticosteroids. Note that several courses of steroid tapering may be necessary as symptoms may worsen when the steroid dose is decreased. For each disorder, attempts should be made to rule out other causes such as metastatic disease or bacterial or viral infection, which might require additional supportive care. The treatment guidelines are intended to be applied when the investigator determines the events to be related to MK3475 (pembrolizumab). Below represent guidelines and not required actions, but investigators are strongly encouraged to follow the below interventions.

A baseline CT scan of the chest should be considered in all patients.

It may be necessary to perform conditional procedures such as bronchoscopy, endoscopy, or skin photography as part of evaluation of the event.

Pneumonitis:

- For Grade 2 events, treat with systemic corticosteroids. When symptoms of Grade 2 events improve to Grade 1 or less, steroid taper should be started and continued over no less than 4 weeks.
- For Grade 3-4 events, immediately treat with intravenous steroids. Administer additional anti-inflammatory measures, as needed. Pembrolizumab should be permanently discontinued for grade 3 or 4 pneumonitis and persistent grade 2 pneumonitis in the event of at least a possibly pembrolizumab-related pneumonitis.
- Add prophylactic antibiotics for opportunistic infections in the case of prolonged steroid administration.

Diarrhea/Colitis:

Subjects should be carefully monitored for signs and symptoms of enterocolitis (such as diarrhea, abdominal pain, blood, or mucus in stool, with or without fever) and of bowel perforation (such as peritoneal signs and ileus).

- All subjects who experience diarrhea/colitis should be advised to drink liberal quantities of clear fluids. If sufficient oral fluid intake is not feasible, fluid and electrolytes should be substituted via IV infusion. For Grade 2 or higher diarrhea, consider GI consultation and endoscopy to confirm or rule out colitis.
- For Grade 2 diarrhea/colitis that persists greater than 3 days, administer oral corticosteroids.
- For Grade 3 or 4 diarrhea/colitis that persists > 1 week, treat with intravenous steroids followed by high dose oral steroids.
- When symptoms of Grade 2 events improve to Grade 1 or less, steroid taper should be

started and continued over no less than 4 weeks (Grade 3-4 events may require permanent discontinuation).

Type 1 diabetes mellitus (if new onset, including diabetic ketoacidosis [DKA]) or \geq Grade 3 Hyperglycemia, if associated with ketosis (ketonuria) or metabolic acidosis (DKA)

- For T1DM or Grade 3-4 Hyperglycemia
 - Insulin replacement therapy is recommended for Type I diabetes mellitus and for Grade 3-4 hyperglycemia associated with metabolic acidosis or ketonuria.
 - Evaluate patients with serum glucose and a metabolic panel, urine ketones, glycosylated hemoglobin, and C-peptide.

Hypophysitis:

- For Grade 2 events, treat with corticosteroids. When symptoms improve to Grade 1 or less, steroid taper should be started and continued over no less than 4 weeks. Replacement of appropriate hormones may be required as the steroid dose is tapered.
- For Grade 3-4 events, treat with an initial dose of IV corticosteroids followed by oral corticosteroids. When symptoms improve to Grade 1 or less, steroid taper should be started and continued over no less than 4 weeks. Replacement of appropriate hormones may be required as the steroid dose is tapered.

Hyperthyroidism or Hypothyroidism:

Thyroid disorders can occur at any time during treatment. Monitor patients for changes in thyroid function (at the start of treatment, periodically during treatment, and as indicated based on clinical evaluation) and for clinical signs and symptoms of thyroid disorders.

Grade 2 hyperthyroidism events (and Grade 2-4 hypothyroidism):

In hyperthyroidism, non-selective beta-blockers (*e.g.* propranolol) are suggested as initial therapy.

In hypothyroidism, thyroid hormone replacement therapy, with levothyroxine or liothyronine, is indicated per standard of care.

- Grade 3-4 hyperthyroidism
 - Treat with an initial dose of IV corticosteroid followed by oral corticosteroids. When symptoms improve to Grade 1 or less, steroid taper should be started and continued over no less than 4 weeks.
 - Replacement of appropriate hormones may be required as the steroid dose is tapered.

Hepatic:

- For Grade 2 events, monitor liver function tests more frequently until returned to baseline values (consider weekly). Treat with IV or oral corticosteroids
- For Grade 3-4 events, treat with intravenous corticosteroids for 24 to 48 hours.
- When symptoms of Grade 2 events improve to Grade 1 or less, a steroid taper should be started and continued over no less than 4 weeks (Grade 3-4 events may require permanent discontinuation).

Renal Failure or Nephritis:

- For Grade 2 events, treat with oral systemic corticosteroids.

- For Grade 3-4 events, treat with intravenous systemic corticosteroids.
- When symptoms of Grade 2 events improve to Grade 1 or less, steroid taper should be started and continued over no less than 4 weeks (Grade 3-4 events may require permanent discontinuation).

Management of Infusion Reactions: Signs and symptoms usually develop during or shortly after drug infusion and generally resolve completely within 24 hours of completion of infusion.

Patients with grade 3-4 IRAEs that completely resolve may be allowed to continue on study on case-by-case basis based on consultation with study chair and CTEP.

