8.1.2 Supportive Care Guidelines

Patients should receive appropriate supportive care measures as deemed necessary by the treating investigator. Suggested supportive care measures for the management of AEs with potential immunologic etiology are also outlined in the table in Section 1.1.3. Where appropriate, these guidelines include the use of oral or IV treatment with corticosteroids as well as additional anti-inflammatory agents if symptoms do not improve with administration of corticosteroids. Note that several courses of steroid tapering may be necessary as symptoms may worsen when the steroid dose is decreased. For each disorder, attempts should be made to rule out other causes such as metastatic disease or bacterial or viral infection, which might require additional supportive care. The treatment guidelines are intended to be applied when the investigator determines the events to be related to pembrolizumab.

Note: If after the evaluation the event is determined not to be related, the investigator does not need to follow the treatment guidance (as outlined below).

It may be necessary to perform conditional procedures such as bronchoscopy, endoscopy, or skin photography as part of the evaluation of the event.

8.1.3 Dose Modification and Toxicity Management for Immune-related Adverse Events Associated with Pembrolizumab

AEs associated with pembrolizumab exposure may represent an immunologic etiology. These immune-related AEs (irAEs) may occur shortly after the first dose or several months after the last dose of pembrolizumab treatment and may affect more than one body system simultaneously. Therefore, early recognition and initiation of treatment is critical to reduce complications. Based on existing clinical study data, most irAEs were reversible and could be managed with interruptions of pembrolizumab, administration of corticosteroids and/or other supportive care. For suspected irAEs, ensure adequate evaluation to confirm etiology or exclude other causes.

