Additional procedures or tests such as bronchoscopy, endoscopy, skin biopsy may be included as part of the evaluation. Based on the severity of irAEs, withhold or permanently discontinue pembrolizumab and administer corticosteroids. Pembrolizumab may cause severe or life-threatening infusion-reactions including severe hypersensitivity or anaphylaxis. Signs and symptoms usually develop during or shortly after drug infusion and generally resolve completely within 24 hours of completion of infusion. Dose modification and toxicity management guidelines for irAEs and infusion reactions associated with pembrolizumab are provided in the table below.

Note that non-irAEs will be managed as appropriate, following clinical practice recommendations.

Dose Modification and Toxicity Management Guidelines for Immune-related AEs and Infusion Reactions Associated with Pembrolizumab

General instructions:				

 For non-endocrine-related severe and life-threatening irAEs, investigators should consider the use of IV corticosteroids followed by oral steroids. Other immunosuppressive treatment should begin if the irAEs are not controlled by corticosteroids. Some non-endocrine irAEs do not require steroids. For example, celiac disease induced by pembrolizumab can be controlled by diet alone. For non-endocrine-related toxicities, pembrolizumab must be permanently discontinued if the irAE does not resolve or the corticosteroid dose is not ≤ 10 mg/day within 12 weeks of the last pembrolizumab-treatment. Generally, when corticosteroids are used, investigators should begin a taper when the irAE is \leq Grade 1 and continue at least 4 weeks. If pembrolizumab has been withheld due to a non-endocrine irAE, pembrolizumab may generally resume after the irAE has decreased to \leq Grade 1 after a corticosteroid taper. 				
irAEs	Toxicity grade (CTCAE V5.0)	Action with pembrolizumab	Corticosteroid and/or other therapies	Monitoring and follow-up
Pneumonitis	Grade 2	Withhold	Administer corticosteroids (initial dose of 1 to 2 mg/kg prednisone or equivalent) followed by taper. Add prophylactic antibiotics for opportunistic infections	Monitor participants for signs and symptoms of pneumonitis. Evaluate participants with suspected pneumonitis with radiographic imaging and initiate corticosteroid treatment
	Recurrent Grade 2, Grade 3 or 4	Permanently discontinue		

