Diarrhea / Colitis	Grade 2 or 3	Withhold	Administer corticosteroids (initial dose of 1 to 2 mg/kg prednisone or equivalent) followed by taper	Monitor participants for signs and symptoms of enterocolitis (i.e. , diarrhea, abdominal pain, blood, or mucus in stool with

	Recurrent Grade 3 or Grade 4	Permanently discontinue	Patients who do not respond to corticosteroids should be seen by a gastroenterologist for confirmation of the diagnosis and consideration of secondary immune suppression	
or without fever) and of bowel perforation (i.e. peritoneal signs and ileus)
 
Specifically assess for celiac disease serologically and exclude Clostridium difficile infection.
 
Participants with \geqGrade 2 diarrhea suspecting enterocolitis should consider GI consultation and performing endoscopy to rule out enterocolitis and assess mucosal severity.
 
Participants with diarrhea/colitis should be advised to drink liberal quantities of clear fluids. If sufficient oral fluid intake is not feasible, fluid and electrolytes should be substituted via IV Infusion.

AST or ALT elevation or Increased Bilirubin	Grade 2 ^a	Withhold	Administer corticosteroids (initial dose of 0.5 to 1 mg/kg prednisone or equivalent) followed by taper	Monitor with liver function tests (consider weekly or more frequently until liver enzyme value returned to baseline or is stable)
	Grade 3 ^b or 4 ^c	Permanently discontinue	Administer corticosteroids (initial dose of 1 to 2 mg/kg prednisone or equivalent) followed by taper	

Type 1 diabetes mellitus (T1DM) or Hyperglycemia	Grade 1 or 2	Continue		Investigate for diabetes. In the absence of corticosteroids or diabetes medication non-adherence, any grade hyperglycemia may be an indication of beta-cell destruction and pembrolizumab-induced diabetes akin to type 1 diabetes. This should be treated as a Grade 3 event. Given this risk, exercise caution in utilizing non-insulin hypoglycemic agents in this setting. After a thorough investigation of other potential causes, which may involve a referral to an endocrinologist, follow institutional guidelines. Monitor glucose control.

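### Section 7.2.3 and the 8.1.3 table conflict on when to start steroids for immune colitis and on whether grade 3-4 hepatic or renal events must end pembrolizumab

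*Combined protocol and SAP*

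**What the plan says.** **Section 7.2.3** covers supportive care for events that the investigator has judged related to pembrolizumab. It describes its own standing: "Below represent guidelines and not required actions, but investigators are strongly encouraged to follow the below interventions". On colitis it has two steroid instructions: "For Grade 2 diarrhea/colitis that persists greater than 3 days, administer oral corticosteroids", and "For Grade 3 or 4 diarrhea/colitis that persists > 1 week, treat with intravenous steroids followed by high dose oral steroids". For pneumonitis the same section says "For Grade 3-4 events, immediately treat with intravenous steroids". Under both the hepatic and the renal entries, a parenthesis says that grade 3-4 events may call for permanent discontinuation.

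**Section 8.1.3** introduces its table with "For suspected irAEs, ensure adequate evaluation to confirm etiology or exclude other causes" and "Based on the severity of irAEs, withhold or permanently discontinue pembrolizumab and administer corticosteroids". It also describes early recognition and early treatment as critical. In the colitis rows pembrolizumab is withheld at grade 2 or 3, and the permanent-stop row reads "Recurrent Grade 3 or Grade 4". The steroid entry is "Administer corticosteroids (initial dose of 1 to 2 mg/kg prednisone or equivalent) followed by taper". For grade 3 or 4 AST, ALT or bilirubin elevation, and for grade 3 or 4 nephritis, the action is permanent discontinuation.

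**Standing of the table.** Section 8.1.1 makes withholding by the table mandatory. Section 8.1.2 calls the table's supportive care measures suggested. Neither mentions 7.2.3.

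**The concern.** A protocol that gives two instructions for the same event should agree with itself or say which one prevails. Here it does neither.

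For grade 3-4 immune colitis, 7.2.3 has no steroid instruction during the first week, while the table has one from the outset. Section 7.2.3 itself warns of bowel perforation, and 8.1.3 stresses early treatment, so the timing is clinically relevant. For grade 3-4 hepatic and renal events, one text leaves permanent discontinuation to judgement and the other requires it. What is at stake is consistent care of patients on the pembrolizumab arm; no estimate or test depends on it.

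**Working it through.** No statistical formula applies. The check sets the two texts side by side and looks for any sentence that ranks them.

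| Item | Section 7.2.3 | Table in 8.1.3 |
|---|---|---|
| Colitis, grade 2: steroids | if it lasts more than 3 days | prednisone 1 to 2 mg/kg or equivalent, no duration condition |
| Colitis, grade 3-4: steroids | if it lasts more than 1 week | same entry, no duration condition |
| Hepatic, grade 3-4: pembrolizumab | permanent stop possible | permanent stop |
| Renal, grade 3-4: pembrolizumab | permanent stop possible | permanent stop |

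1. **Order of the colitis triggers.** 7 days - 3 days = 4 days longer for the more severe grade. Elsewhere 7.2.3 does not work this way: grade 3-4 pneumonitis is treated at once, and the hepatic and renal steroid instructions carry no duration condition.

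2. **Reading of the table.** In the extracted text the colitis steroid entry sits beside the grade 2 or 3 row. I read it as a cell that extends to the grade 4 row. The lead-in sentence, which ties steroids to severity, supports that reading, and the grade 2 and first grade 3 comparison does not depend on it.

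3. **Does the difference reflect time for diagnosis?** Not as written. The 7.2.3 guidance is meant for events already judged related to pembrolizumab, so its waiting periods follow attribution. The table handles diagnosis separately, by asking for evaluation and for exclusion of *Clostridium difficile*, without a fixed wait.

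4. **Does either text outrank the other on steroids?** No. Section 7.2.3 is optional but strongly encouraged; 8.1.2 calls the table's measures suggested. The mandatory sentence in 8.1.1 concerns withholding pembrolizumab, not starting steroids.

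5. **Is the hepatic and renal stop discretionary in the table?** Footnote d, which leaves withholding or stopping to the investigator, is attached to the diabetes, hypophysitis and hyperthyroidism entries. It is not attached to the hepatic or nephritis rows; the hepatic footnotes only define the grades.

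6. **Does either text outrank the other on dosing?** By implication the table does, from the mandatory wording in 8.1.1 and the title of Section 8. No sentence states it.

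**The case against.** The best defence is that sites hold one protocol, not two. Section 7.2.3 disclaims any binding force, opens by deferring to the treating investigator, and follows directly on 7.2.2, which refers readers to the table. Nothing prevents steroids on day 1, and a clinician told to treat grade 2 after 3 days would hardly wait longer at grade 3. A persistence window might also be deliberate: diarrhea is listed for cytarabine and both anthracyclines, infection must be ruled out, and 7.2.1 asks that high-dose steroids be avoided where possible.

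Much of this stands. It keeps the severity low, and it means that the 4-day gap is a difference between advisory triggers, not an estimated treatment delay. It does not resolve the steroid conflict, because the table's supportive care is also only suggested. If a window was intended, the table should carry it as well.

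Three stronger readings are tempting, and the documents do not support them:

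- *That the texts also conflict on stopping for colitis.* They do not. Saying that grade 3-4 colitis may call for a permanent stop fits a table that withholds at a first grade 3 and stops at grade 4 or recurrent grade 3.
- *That the sentence allowing patients with fully resolved grade 3-4 immune events to continue lets a site restart pembrolizumab on its own.* In 7.2.3, 7.3 and 7.5 it requires consultation with the study chair and CTEP. Its wording could be clearer, but that is optional.
- *That the wrong section numbers pointing to the dosing rules are a safety fault in themselves.* They are clerical, mostly a one-section numbering shift.

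**Conclusion.** The point holds in two parts. On colitis steroids, 7.2.3 and the 8.1.3 table give different timing, with equal advisory standing and no rule to choose between them. On grade 3-4 hepatic and renal events, 7.2.3 is softer than the table; mandatory wording in 8.1.1 points to the table, but precedence is left to inference.

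The guidance is wrong as written, in that it conflicts with itself on a safety matter, and the severity is low. A reader might infer that the early safety rule or the primary comparison is affected. The documents give nothing from which such an effect could be derived, and none is claimed on power, the safety rule or the analysis. Nor is a number of affected patients projected: the documents give no rate of pembrolizumab-related colitis for this regimen. The colitis counts that section 11.1.3 cites (one grade 3 and one grade 4 event among 44 patients, regardless of cause) come from nivolumab with a different chemotherapy schedule.

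**What to change.** 1. In 7.2.3, replace the 3-day and 1-week colitis conditions with the table's severity-based steroid wording, to apply after evaluation to exclude infection and other causes.
2. In 7.2.3, replace the open wording on grade 3-4 hepatic and renal events with the table's permanent stop, subject to the existing case-by-case exception with study chair and CTEP consultation.
3. State once, in 7.2.3 or 8.1.1, that the 8.1.3 table governs pembrolizumab dosing and the management of immune-related events.

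The stale section numbers can be corrected in the same amendment as an editorial matter. The cost is protocol wording only, with no change to sample size, visits or data collection.

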7.2.4 Concomitant treatments with cytarabine anthracycline chemotherapy

During the induction cycles, G- and GM-CSF may be used only in case of prolonged neutropenia or neutropenic sepsis if non-blastic aplasia is obtained; there will be no such constraints in subsequent cycles. Use of growth factors during consolidation and maintenance is allowed but discouraged.

Antibiotics and antifungals can be given according to institutional rules. For other drugs, refer to individual product US package inserts. Patients should receive all necessary supportive care, including blood product transfusions, erythropoietin, and pain medications.

7.2.5 Tumor Lysis Syndrome Monitoring and Prophylaxis

Patients with a low risk of developing tumor lysis syndrome (TLS) should be monitored for development of TLS and complications; normal hydration and no prophylaxis for hyperuricemia should be given except in cases of signs of metabolic changes, bulky and/or advanced disease and/or high proliferative disease, in which case allopurinol should be added.

Patients with an intermediate risk of developing TLS should be monitored for TLS and complications, administered increased hydration (3 L/m² per day) and administered allopurinol (100–300 mg, by mouth [PO], every 8 hours [Q8H], daily) without the need for alkalinization.

In patients with high risk of developing TLS, frequent monitoring should be performed, increased hydration (3 L/m² per day), unless evidence of renal insufficiency and oliguria, and rasburicase (0.1–0.2 mg/kg) for one dose and repeated only if clinically necessary. In patients with a prior history of glucose-6-phosphate dehydrogenase, rasburicase is contraindicated and allopurinol should be utilized instead of rasburicase.

Furthermore, management of hyperkalemia and/or hyperphosphatemia should be managed as per institutional routine. Lastly, patients who develop laboratory TLS who were originally classified as either low or intermediate risk, should receive rasburicase unless clinically contraindicated.

